8.1 Cognitive Evaluations

8.1.1 Mini-Mental State Examination (MMSE)

The MMSE (Folstein et al., 1975) is a brief, frequently used screening instrument for AD drug studies. The MMSE evaluates orientation, memory, attention, concentration, naming, repetition, comprehension, and ability to create a sentence and to copy two overlapping pentagons. A lower score indicates more cognitive impairment. The highest score is 30. Participants with MMSE scores outside the range of 12-26 (inclusive) will not be included in this study. This test will be administered at Screening, Baseline, and Week 24.

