3.4 Secondary Endpoints

- Change from Baseline ¹⁸F-AV-1451 Tau PET imaging SUV_r results to Week 24 results
- Change from Baseline to Week 24 on the scores of MMSE, ADAS-Cog 11, CGIC
- Change from Baseline to Week 24 on the scores of NPI and ADCS-ADL
- Change from Baseline to Week 24 on the scores of Digit Span test, COWAT and QoL-AD/Study Partner
- Safety and tolerability as measured by incidence of adverse events/serious adverse events (AEs/SAEs) clinical lab test data, vital signs, 12-lead EKG data
- Proportion of subjects with adverse events, serious adverse events and adverse events leading to discontinuation over the 24-week double blind treatment period
- Proportion of subjects with laboratory abnormalities
- Proportion of subjects with ECG abnormalities

[figure not shown]

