4. STUDY DESIGN

This is a 24 week, Phase II, randomized, double blind, placebo controlled, parallel group, proof-of-concept three-site study, to evaluate the effect of rasagiline in the regional brain metabolism on FDG PET in patients with mild to moderate Alzheimer's disease.

The study consists of two phases: a 24-week double blind placebo controlled treatment period with a 4-week follow-up period. Patients will be randomized to a 1:1 ratio at Baseline to receive rasagiline or matching placebo treatment.

The study drug will be given as 0.5 mg dose once daily for the first 4 weeks then increased to 1 mg dose daily tablet for the next 20 weeks. A total of 50 subjects will be enrolled and will be randomized to a 1:1 ratio. Twenty-five participants will receive rasagiline and the other 25 will receive matching placebo for the 24-week treatment period.

Figure 5. **Research Schematic**

Visit 1 – Screening visit (within a 60-day period); MRI, FDG PET and ¹⁸F-AV-1451 Tau imaging

Visit 2 – Baseline (Week 1)

Visit 3 Week 4; increase dose from 0.5 mg QD to 1 mg QD

Visit 4 Week 8

Visit 5 –Week 24; blood draws, FDG PET & ¹⁸F-AV-1451 Tau imaging, end of treatment

Visit 6 – Follow-up Visit/ Week 28; end of study/early discontinuation

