7. DESCRIPTION OF STUDY VISITS

7.1 Visit 1 – Screening (Days -60 to -1)

Subjects will undergo all screening procedures within 60 days prior to baseline visit to confirm the study eligibility.

The following activities will be completed:

- Obtain IRB approved written informed consent from the subject and the subject's legal representative in accordance with regulation before initiating any procedures for both the main protocol and the **¹⁸F-AV-1451 imaging companion** protocol
- Assess inclusion and exclusion criteria
- Obtain demographic data
- Obtain medical history and review medications
- Obtain history of prior procedures (radiation/PET)
- Record prior medication within the last 3 months
- Obtain Ohio State University Traumatic Brain Injury Identification Method (OSU TBI-ID) Questionnaire for the **¹⁸F-AV-1451 TAU imaging companion protocol**.
- Perform Mini Mental State Examination (MMSE)
- Perform physical and neurological examinations
- Record orthostatic vital signs, body weight and height
- Obtain standard single 12 lead EKG
- Collect non-fasting blood sample for routine laboratory test including:
 - Hematology
 - Blood chemistry
 - Liver function
 - TSH
 - B12
- Collect urine sample for screening urinalysis (UA)
- Obtain MRI: T1 sequence and two-dimensional T2*-GRE to detect micro-hemorrhages and T2 FLAIR sequences to identify ARIA-E
- Obtain fluorodeoxyglucose (FDG) PET imaging
- Obtain **¹⁸F-AV-1451** Tau imaging pending positive FDG PET imaging results

The screening visit MRI, FDG PET imaging and **¹⁸F-AV-1451** Tau PET imaging visits will be done on separate visits.

POST ¹⁸F-AV-1451 TAU IMAGING FOLLOW-UP PHONE CALL

A follow-up phone call to the participant or the caregiver will be conducted between 2 and 3 business days after the imaging visit, but not before 48 hours post-injection, to confirm participant well-being and to collect information about any new adverse events. If both of these days are not business days, the follow-up phone call can occur the following business day.

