8.4 Longitudinal Region of Interest based Evaluation

The SUVrs calculated for each subject will be compared using t-tests, within groups and across groups, as shown in Table 4 below. While the pre-identified reference regions for testing will be whole brain, cerebellum, and pons, an alternate reference region may be identified through the use of NPAIRS multivariate analysis and applied.

9 Analysis of Clinical Measures

In general, analyses will incorporate the Intent-to-Treat principle, namely, all randomized participants will be included in the analysis. Analyses for all efficacy outcomes will be guided by exploratory analyses. All results will be reported as point estimates (odds ratios or mean differences across groups, as appropriate) and interval estimates (95% confidence intervals) with two-sided p-values denoting statistical significance. Since this is an early phase safety and preliminary efficacy study, no adjustments for multiple comparisons will be made and a p-value of 0.05 will be considered statistically significant.

All clinical measures (MMSE, ADAS-Cog11, ADCS-ADL, NPI, Digit-Span, COWAT and QoL) over 24 weeks will be analyzed using the linear mixed-effects regression model to assess the difference in the rate of change between the two treatment arms. The model will include scores as the dependent variable and time, treatment assignment, time-by-treatment interaction term and any variables determined to be confounders as independent variables. Time will be treated as a continuous variable. An unstructured variance-covariance structure will be used. A significant treatment effect will be concluded if the p-value for the time-by-treatment interaction term in the model is ≤ 0.05 . Sensitivity analyses will be conducted by analyzing the data using response profiles. Here, time will be treated as a categorical variable. The analysis of response profiles will allow us to characterize the patterns of change in the mean response over time in the treatment groups.

To assess the rate of change in the ADCS-CGIC over 24 weeks, a generalized estimating equations (GEE) model for binary data will be used. Because very few change scores were at the extreme ratings of marked worsening, moderate worsening, marked improvement, or moderate improvement are expected in this study, the ADCS-CGIC will be treated as a dichotomous dependent variable (no change/improved and worse).

The analyses will be repeated in the PP population.

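### MMSE is scored twice before the first dose, but the planned MMSE comparison adjusts for neither score; entering both as covariates is an inexpensive, probably modest gain in precision

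*Protocol*

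**What the plan says.** **Schedule.** Protocol 8.1.1 sets three MMSE assessments: "This test will be administered at Screening, Baseline, and Week 24". The Schedule of Activities (Protocol 7.8, Table 2) agrees and shows no MMSE at Weeks 4, 8 or 28. The two pre-dose scores can be up to 60 days apart: "Subjects will undergo all screening procedures within 60 days prior to baseline visit to confirm the study eligibility" (Protocol 7.1).

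**Stated role of the score at entry.** "Participants with MMSE scores outside the range of 12-26 (inclusive) will not be included in this study" (Protocol 8.1.1).

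**Endpoint.** Protocol 3.4 lists "Change from Baseline to Week 24 on the scores of MMSE, ADAS-Cog 11, CGIC".

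**Analysis.** SAP section 9: "All clinical measures (MMSE, ADAS-Cog11, ADCS-ADL, NPI, Digit-Span, COWAT and QoL) over 24 weeks will be analyzed using the linear mixed-effects regression model". The model has time (continuous), treatment, their interaction and "any variables determined to be confounders as independent variables", with unstructured covariance. The test is on the interaction. The Screening MMSE is neither named nor excluded. For the clinical measures, "no adjustments for multiple comparisons will be made and a p-value of 0.05 will be considered statistically significant".

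**Size.** "Twenty-five participants will receive rasagiline and the other 25 will receive matching placebo" (Protocol 4).

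**The concern.** A single MMSE score varies from one occasion to the next for reasons unrelated to the patient's underlying state. In a change score, all of that variation in the Baseline measurement enters the treatment comparison. The usual remedy is to adjust the Week 24 score for what was measured before randomisation. Here every randomised patient should have two such scores.

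The other repeated scales (ADAS-Cog 11, ADCS-ADL, NPI, Digit Span, COWAT) also have scores at Weeks 4 and 8 to support the model. MMSE has none, so its second pre-dose score is the only extra MMSE information available.

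What is at stake is the width of the MMSE confidence interval. Neither validity nor type I error is in question.

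**Working it through.** **1. What the plan's model does for MMSE.** If analysis over 24 weeks starts at Baseline, MMSE contributes two time points. With time, treatment, their interaction, unstructured covariance and complete data, the interaction (scaled to 24 weeks) equals the difference between arms in mean change. A simulated data set with 25 per arm confirmed this: the mixed model and the two-sample comparison of change scores gave the same estimate and the same standard error. Baseline is an outcome in this model, so it is not adjusted for.

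**2. Inputs.** The documents give no SD, reliability, correlation or power figure for MMSE, so there is no plan figure to reproduce. (The sample-size figures in Protocol 11.3 concern FDG.) Assumed values:
- measurement SD e = 1.5–2.5 points
- true-score SD at Screening T = 3–4
- SD of true 24-week change d = 2–3
- true change before Baseline accruing at the same rate over a gap of 0 to 60 days, so its variance is g = d² × gap/168

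**3. Formulas (variance per patient).** Let B = T² + g be the true-score variance at Baseline.
- Change from Baseline (the plan): 2e² + d²
- Adjusted for Baseline only: B + d² + e² − B²/(B + e²)
- Adjusted for Baseline and Screening separately: B + d² + e² − c′S⁻¹c, where c = (T², B) and S has diagonal (T² + e², B + e²) and off-diagonal T²

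**4. Example: T = 4, e = 2, d = 2.5.**
- Plan: 2×4 + 6.25 = 14.25.
- No gap. Baseline only: 26.25 − 256/20 = 13.45. Both scores: 26.25 − 256/18 = 12.03. The reduction against the plan is 15.6%. Screening's own increment is 1 − 12.03/13.45 = 10.6%.
- 60-day gap: g = 6.25 × 60/168 = 2.23 and B = 18.23. Baseline only: 28.48 − 14.95 = 13.53. Both scores: 28.48 − 15.93 = 12.55. The reduction against the plan is 11.9%. Screening's increment is 7.2%.

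**5. Full range of assumptions (reduction in variance).**

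| | No gap | 60-day gap |
|---|---|---|
| Baseline only, against the plan | 2.1–15.5% | 1.8–14.2% |
| Both scores, against the plan | 8.9–23.8% | 5.0–20.8% |
| Both scores, against Baseline only | 6.1–12.7% | 2.6–10.5% |
| Equal-weight mean of the two, against Baseline only | 6.1–12.7% | −0.2 to 10.2% |

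**6. Less favourable correlations.** These are also assumed, with equal SDs, in the order Screening–Baseline, Baseline–Week 24, Screening–Week 24. The plan's variance is 2 − 2r for the Baseline–Week 24 correlation r. Baseline-only variance is 1 − r².

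| Correlations | Both, against plan | Both, against Baseline only | Mean, against Baseline only |
|---|---|---|---|
| 0.85, 0.75, 0.70 | −15.3% | −3.2% | −1.3% |
| 0.90, 0.80, 0.75 | −11.2% | −1.3% | +2.2% |
| 0.95, 0.80, 0.76 | −10.0% | 0.0% | +4.4% |
| 0.90, 0.80, 0.70 | −10.5% | −0.6% | +13.3% |

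The mean can do worse than Baseline alone. Two separate covariates cannot raise the residual variance.

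**7. Cost of estimating the coefficients.** With N = 50 and p roughly normal covariates, chance imbalance multiplies the expected variance by (N − 3)/(N − p − 3). That is 47/46 = 1.022 for one covariate and 47/45 = 1.044 for two. The 5.0–23.8% range against the plan then becomes about 1–20% (0.950 × 1.044 = 0.992; 0.762 × 1.044 = 0.796). Screening's 2.6–12.7% becomes about 0.5–11% (factor 46/45 = 1.022).

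**8. Selection at entry.** Simulations that truncated the Screening score to 12–26 gave standard-error ratios, for adding Screening to a Baseline-adjusted analysis, of about 0.92 (all correlations 0.8) and 0.99 (0.90, 0.80, 0.75).

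**The case against.** **Change from Baseline is conventional.** This stands. It is the reference for every scale in Protocol 3.4, and nothing here is a contradiction, a bias or an inflated error rate. The Screening score also has a job as the entry check.

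**A reader might infer that the SAP discards the Screening score.** The documents do not support that. The protocol endpoint is explicit about Baseline, but the SAP is silent on Screening and leaves covariates open. That silence still needs settling: with time continuous, admitting a pre-Baseline record would change the fitted MMSE slopes.

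**A reader might also credit the whole gain to the second score.** That is wrong. Baseline adjustment alone gives about 2–15% on the assumed grid. The 6–13% increment for Screening requires no true change between the two visits, although the same calculation assumes real change afterwards. Allowing change over 60 days lowers the increment to about 3–10%, and the correlations in step 6 bring it to 0–3%. Some of those sets are extreme: under a simple decay-plus-error model, reliability is the product of the first two correlations divided by the third, which gives 0.91, 0.96, 1.00 and an impossible 1.03. A small increment nevertheless cannot be excluded.

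**Regressing Week 24 MMSE drops patients without that score.** True, and the early-discontinuation visit does not collect MMSE. The practical loss is small, because such patients have no post-baseline MMSE and add little to the planned interaction either.

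**Selection on 12–26 and regression to the mean.** These act alike in both randomised arms. They limit the gain and do not bias the comparison.

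**Conclusion.** The point holds as an optional gain in efficiency. For MMSE the plan amounts to an unadjusted comparison of change scores, on the natural reading that the model starts at Baseline. Adjusting for both pre-randomisation scores lowers the variance of the arm difference by about 5–24%, or 2.5–13% in standard error, before the roughly 4% cost of estimating two coefficients. Screening adds about 3–13% to what Baseline adjustment achieves. If Screening tracks Week 24 poorly it adds close to nothing, and the extra coefficient could then cost about 2%.

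All of these figures rest on assumed SDs and correlations, so the documents cannot show that any particular amount of precision is lost. MMSE is an unpowered secondary endpoint, and Protocol 3.2 names ADAS-Cog 11, not MMSE, for cognition. The FDG primary analysis is unaffected.

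**What to change.** In SAP section 9, for MMSE only, add:

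*Week 24 MMSE will be regressed on treatment, Baseline MMSE and Screening MMSE (as separate covariates); the arm difference is reported with its 95% CI.*

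Keep the planned mixed model on all randomised patients as a sensitivity analysis, and state whether the Screening record enters it. Keep change from Baseline as a descriptive summary. Use separate covariates in place of the mean of the two scores, because the mean can lose precision when the older score is less informative.

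**Cost.** One or two sentences in a SAP still marked as a draft, settled before unblinding, with no new data. The analysis spends two covariate degrees of freedom, and the main MMSE result is limited to patients with a Week 24 score.

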8.1.2 Alzheimer's Disease Assessment Scale-Cognitive 11 (ADAS-Cog 11)

The ADAS-Cog (Rosen et al., 1984) is a psychometric instrument that evaluates memory, attention, reasoning, language, orientation, and praxis. A higher score indicates more impairment. Scores from the original portion of the test range from 0 (best) to 70 (worse). A positive change indicates cognitive worsening. This test will be administered at Baseline, Weeks 4, 8, 24 and 28.

8.2 Clinical and Functional Evaluations

8.2.1 Clinician Global Impression of Change (CGIC)

This is a rating scale of global impression of change. The CGIC is a clinician assessment of change in the patient's functioning administered to the patient and the caregiver. This test will be conducted at Baseline, Week 4, Week 24, and Week 28.

8.2.2 Alzheimer's Disease Cooperative Study - Activities of Daily Living (ADCS-ADL)

The ADCS-ADL is an activities-of-daily-living inventory developed by the ADCS to assess functional performance in participants with AD (Galasko et al., 1997). Using a structured interview format, study partners are queried as to whether participants attempted each item in the inventory during the past 4 weeks and their level of performance. The ADCS-ADL scale discriminates well between normal participants and those with mild AD and it has good test-retest reliability. The ADCS-ADL includes some items from traditional basic ADL tests (e.g., grooming, dressing, walking, bathing, feeding, toileting) as well as instrumental (complex) activities of daily living (e.g., shopping, preparing meals, using household appliances, keeping appointments, reading). This test will be administered at Baseline, Weeks 4, 8, 24, and 28.

8.2.3 Neuropsychiatric Inventory (NPI)

The behavioral outcome measure for this trial is the NPI (Cummings, 1997). The NPI is a well validated, reliable, multi-item instrument to assess psychopathology in AD based on interview with the study partner. The NPI evaluates both the frequency and severity of 10 neuropsychiatric disturbances. Frequency assessments range from 1 (occasionally, less than once per week) to 4 (very frequently, once or more per day or continuously) as well as severity (1=mild, 2=moderate, 3=severe). The overall score and the score for each subscale are the

product of severity and frequency. This test will be administered at Baseline, Weeks 4, 8, 24 and 28.

8.2.4 Controlled Oral Word Association Test (COWAT)

This is a 3-4 minute measure of phonological fluency that indexes a number of the processes described as ‘executive function,’ including, planning, strategy and working memory. Study participants are instructed, “*I want to see how many words you can say beginning with a certain letter in one minute. Don’t say proper nouns or numbers or the same word with a different ending and try not to repeat yourself. The letter is ‘-, begin.’*” The study participant’s responses are recorded on the worksheet. Study participants are then given an additional one minute for each of two different letters using similar instructions.

Responses are then judged for their acceptability (example for the use of proper nouns, numbers, repetitions and stem word with a different ending). The score is the total number of acceptable words for the three trials combined. A higher score represents better performance. This test will be administered at Baseline, Week 4, Week 8, Week 24, and Week 28.

8.2.5 Digit Span

The Digit Span Test is adopted from the Wechsler Memory Scale and consists of repetition of increasing long strings of digits presented at 1 per second as read by the examiner and repeated by the subject. A normal Digit Span is 7 digits forward +/- 2 digits. The score is the maximum number of digits the patient can repeat until they fail twice in a row. The reverse digit span is identical to the forward digit span except that the patient repeats the presented digits in reverse order. A normal reverse digit span is 5 +/- 1 digit. The score is the maximum number of digits the patient can repeat in reverse order until they fail twice in a row. This test will be administered at Baseline, Weeks 4, 8, 24, and 28.

8.2.6 QoL-AD/Study Partner

The QoL-AD is a commonly used 13 item QoL scale that assesses items specific to QoL in patients with cognitive impairment. It is administered to the research partner with answers for the patient. This assessment will be performed at the Baseline and Week 24 visits.

8.2.7 Ohio State University Traumatic Brain Injury Identification Method (OSU TBI-ID) Questionnaire

Traumatic brain injury (TBI) can lead to tau protein deposition in the brain and these changes could be visualized on ¹⁸F-AV-1451 Tau imaging. To account for any contribution of TBI to the imaging findings, the Ohio State University (OSU) TBI Identification Method (OSU TBI-ID) is being utilized. The OSU TBI-ID is a standardized procedure for eliciting a person’s lifetime history of TBI via a 3-5 minute structured interview. While recall by an individual, parent or significant other is not ideal for determining lifetime exposure to potentially damaging brain injury, self-report remains the gold standard for research and clinical use. Physicians, nurses and mental health professionals working with military personnel need this tool to elicit a complete history of TBI. The validity of the OSU TBI-ID is not based on elicitation of a veridical accounting of a person's lifetime history of TBI. Instead, the OSU TBI-ID provides data for calculating summary indices reflecting the likelihood that consequences have resulted from lifetime exposure to TBI. Initial validation research has supported the psychometric qualities of these summary indices. Reliability has been demonstrated by both inter-rater and test/re-test reliability (Corrigan & Bogner, 2007; Bogner & Corrigan, 2009). Predictive validity has been shown by the relationship between indices of lifetime history and

measures of cognitive performance, affective status, interpersonal functioning and aggression (Corrigan & Bogner, 2007; Bogner & Corrigan, 2009). Summary indices from the OSU TBI-ID can be used in both research and clinical care (35, 36). This assessment will be completed at the Screening and Week 24 visits.

9. Study Methods

9.1 Safety Assessments

At each study visit, adverse events (AEs) and serious adverse events (SAEs) will be reviewed; vital signs and weight will be done for safety assessments. Hematology, blood chemistry, and liver function tests will be collected at Screening visit and Week 24.

Potential adverse events will be reviewed by the Principal Investigator and documented. Adverse events include signs or symptoms that may or may not be related to study medication, abnormalities detected on physical examination, or clinically significant laboratory abnormalities. Adverse events will be graded (mild: causing no limitation of usual activities; moderate: causing some limitation of usual activities; severe: causing inability to carry out usual activities) and recorded on case report forms.

9.2 Concomitant Medications

Concomitant medications will be recorded at each visit based on the study partner interview and any other available information. After randomization, initiation of any excluded medication, or change in permitted agents will be discouraged. However, follow-up of all participants, regardless of compliance with medication restrictions, will be continued in order to maximize the data available for the intent to treat analysis.

Initiation during the study of medications which are excluded because of confounding effects on cognitive outcomes (such as sedating or anticholinergic medications) is discouraged, but will not require termination of study drug or exclusion from the ITT analysis. Cessation or change of anti-dementia therapies during the study is also discouraged, but will also not prevent continued participation in the protocol or inclusion in the intent to treat analysis.

